### 1.2.4 Acalabrutinib and Thrombus Formation

Ibrutinib is associated with an increased risk of bleeding (Kamel 2015). Hence, the effects of acalabrutinib and ibrutinib were evaluated on human platelet-mediated thrombus formation by using the in vivo human thrombus formation in VWFHA1 murine model, which has been previously described (Chen 2008). The in vivo function of platelets isolated from

blood of healthy volunteers (n=5), CLL patients treated with 420 mg once per day (QD) ibrutinib (n=5), or CLL patients treated with 100 mg BID acalabrutinib (n=3) was evaluated in the VWFHA1 model. Results from this study showed a reduction in platelet-vessel wall interactions of platelets from ibrutinib-treated CLL patients, but not of those from CLL patients treated with acalabrutinib (Byrd 2016).

#### Figure 3 In Vivo Thrombus Formation

Platelets from patients treated with ibrutinib 420 mg once per day (QD) (n=5) or acalabrutinib 100 mg twice per day (BID) (n=3) were evaluated for their ability to support thrombus formation in laser injured arterioles of VWFHA1 mice. Freshly isolated platelets from healthy volunteers (n=5) were used as non-drug treated controls. A minimum of 4 arterioles per mouse was used to assess thrombus formation for each patient/volunteer sample. Thrombus size as a function of time is provided in the figure (shading denotes standard error of the median).

### 1.2.5 Safety Pharmacology

In vitro and in vivo safety pharmacology studies with acalabrutinib have demonstrated a favorable nonclinical safety profile.

When screened at 10 µM in binding assays evaluating interactions with 80 known pharmacologic targets such as G-protein–coupled receptors, nuclear receptors, proteases, and ion channels, acalabrutinib shows significant activity only against the A3 adenosine

receptor; follow-up dose-response experiments indicated a half-maximal inhibitory concentration ( $IC_{50}$ ) of 4.6  $\mu$ M, suggesting a low clinical risk of off-target effects.

The in vitro effect of acalabrutinib on human ether-à-go-go-related gene (hERG) channel activity was investigated in vitro in human embryonic kidney cells stably transfected with hERG. Acalabrutinib inhibited hERG channel activity by ~25% at 10  $\mu$ M, suggesting a low clinical risk that acalabrutinib would induce clinical QT prolongation as predicted by this assay (see the acalabrutinib IB for a summary of the thorough QT study in humans).

Acalabrutinib was well tolerated in standard in vivo Good Laboratory Practices (GLP) studies of pharmacologic safety. A functional observation battery in rats at doses through 300 mg/kg (the highest dose level) revealed no adverse effects on neurobehavioral effects or body temperature. A study of respiratory function in rats also indicated no treatment-related adverse effects at doses through 300 mg/kg (the highest dose level). In a cardiovascular function study in awake telemeterized male beagle dogs, single doses of acalabrutinib at dose levels through 30 mg/kg (the highest dose level) induced no meaningful changes in body temperature, cardiovascular, or electrocardiographic (including QT interval) parameters. The results suggest that acalabrutinib is unlikely to cause serious off-target effects or adverse effects on critical organ systems.

# 1.2.6 Drug-drug Interaction Potential

For more detailed information on drug-drug interaction potential for acalabrutinib, refer to the acalabrutinib IB.

Please refer to Section 3.10.7 for guidance on drugs that may cause drug-drug interactions.

### 1.2.7 In Vivo General Toxicology

The systemic toxicity of acalabrutinib has been fully investigated in repeat-dose sub-chronic studies in mice, rats, and dogs. The pivotal GLP studies were 28- and 91-day repeat-dose studies in rats and dogs, each with recovery periods to assess the reversibility of observed changes.

In rats, 100 mg/kg/day was selected initially to represent the highest non-severely toxic dose; however, in subsequent studies the 100 mg/kg/day dose level was determined to be a no observable adverse effect level (NOAEL). In rats, the target organs of toxicity were the kidney, liver, and heart.

The NOAEL in the dog was 30 mg/kg/day; dose levels higher than 30 mg/kg/day were not tolerated. In dogs, the target organs of toxicity, observed only at doses exceeding the MTD, were the kidney and liver. Heart findings were also observed in 2 dogs with kidney toxicity, which were interpreted as possibly secondary to uremia, as has been reported for this species.

In rats and dogs, no adverse electrocardiogram (ECG) or histopathologic cardiovascular effects were noted at the planned conclusion of the sub-chronic studies or in the rat chronic toxicity study. However, in 5 of 6 rats from the 4-week study that died early, slight to moderate necrosis of the myocardium and/or white blood cell infiltration/inflammation of the myocardium were noted on microscopic examination of the hearts.

#### 1.3 PEMBROLIZUMAB

Pembrolizumab is a potent humanized immunoglobulin G4 (IgG4) monoclonal antibody (mAb) with high specificity of binding to the PD-1 receptor, thus inhibiting its interaction with PD-L1 and PD-L2. Based on nonclinical in vitro data, pembrolizumab has high affinity and potent receptor blocking activity for PD-1. Pembrolizumab has an acceptable nonclinical safety profile and is in clinical development as an IV immunotherapy for advanced malignancies. KEYTRUDA® (pembrolizumab) is indicated for the treatment of patients across a number of indications. For more details on specific indications refer to the pembrolizumab IB.

#### 1.4 CLINICAL EXPERIENCE

Acalabrutinib has been studied in a broad range of clinical studies, including subjects with hematologic malignancies and solid tumors. No new safety concerns were identified for acalabrutinib monotherapy based on safety data available to date. The safety data of acalabrutinib monotherapy are consistent among studies. For more detailed and updated information on the clinical experience for acalabrutinib, refer to the acalabrutinib IB. See the KEYTRUDA package insert for details about clinical experience with pembrolizumab.

### 1.4.1 Pharmacokinetics and Pharmacodynamics of Acalabrutinib

**ACE-HV-001** was a pharmacokinetic (PK)/PD, dose-ranging, food-effect, and drug-drug interaction study evaluating BID and QD dosing for 1 or 2 days in healthy volunteers. This study evaluated the PK/PD of acalabrutinib at various dose levels and regimens. The starting dose for acalabrutinib was 2.5 mg BID. This study has been completed and no

adverse laboratory, vital signs, or ECG findings were observed (2.5 to 50 mg BID; 50 to 100 mg QD). Three AEs related to study drug were reported. Each AE was Grade 1 and resolved without treatment. The AEs were constipation (2.5 mg BID), feeling cold (75 mg QD), and somnolence (75 mg QD).

In Part 1, PK properties of acalabrutinib were evaluated after oral administration of 2 daily divided doses of 2.5 to 50 mg and a single dose of 100 mg. Of the 30 subjects evaluated, all observed systemic concentrations of acalabrutinib. Acalabrutinib plasma time to maximum concentration  $(T_{max})$  values were between 0.5 and 1.0 hour for all dose cohorts and were independent of dose level. The increase in mean maximum observed plasma concentration  $(C_{max})$  values was greater than dose proportion based on the increases of  $C_{max}$  from the first dose administered. When evaluating area under the curve from time 0 to 12-hour timepoint (AUC0-12), from time 0 to 24-hour timepoint (AUC0-24), or from time 0 to infinity (AUC0-inf) the mean values increased in a dose-proportional manner based on the increases of the total dose administered. Mean half-life ( $t_{1/2}$ ) values ranged from 0.97 to 2.1 hours and appeared to decrease as the dose increased. The mean calculated oral clearance (CL/F: 165 to 219 L/h) and volume of distribution values (Vz/F: 233 to 612 L) appeared to be independent of the dose administered.

Acalabrutinib was not detected in the urine of subjects receiving the 2.5- or 5.0-mg BID doses of acalabrutinib. Acalabrutinib was detected in urine of other subjects (0.4% to 0.6% of dose) and amounts increased in a dose-dependent manner.

In Part 2, the effect of food on the PK of acalabrutinib (75 mg) after a single oral administration was evaluated in 6 men and 6 women. Median acalabrutinib plasma  $T_{max}$  values were increased in the fed state (2.5 hours) relative to the fasted state (0.5 hour). The mean plasma acalabrutinib  $C_{max}$  fed values decreased to 27.3% of the  $C_{max}$  values observed in the fasted state. In contrast, the relative AUC exposure of acalabrutinib remained mostly unchanged in both states. This decrease in exposure is not clinically significant; therefore, acalabrutinib can be taken without regard to meals.

In Part 3, the effect of itraconazole on the PK of acalabrutinib (50 mg) after a single oral administration was evaluated in 17 subjects. No difference in acalabrutinib  $T_{max}$  values was observed in the presence or absence of itraconazole.

Mean acalabrutinib exposures (as assessed by  $C_{max}$ ,  $AUC_{0-last}$ ,  $AUC_{0-24}$ , and  $AUC_{0-inf}$ ) increased in the presence of itraconazole. The mean plasma acalabrutinib  $C_{max}$  values increased 3.7-fold in the presence of itraconazole. The mean plasma  $AUC_{0-last}$ ,  $AUC_{0-24}$ , and  $AUC_{0-inf}$  values also increased between 4.9- to 5.1-fold in the presence of itraconazole. Mean CL/F and Vz/F values decreased in the presence of itraconazole (CL/F: 217 vs 44 L/h; Vz/F: 1190 vs 184 L). No differences in t1/2 were observed (3.3 vs 2.5 hours).

The PD of acalabrutinib was evaluated using a BTK occupancy assay and correlated with a functional assay that determines the level of BTK inhibition by measuring expression of CD69 and CD86 on B cells. A dose-dependent increase in BTK occupancy and corresponding decrease in CD69/86 expression was observed in this study. Full BTK occupancy ( $\geq$ 90%) and complete CD86 and CD69 inhibition ( $\geq$ 90%) occurred at the 75- and 100-mg single dosed cohorts 1 to 3 hours after administration. However, only the 100-mg cohort maintained high BTK occupancy (91.5%) and high BCR functional inhibition (CD86: 86 ±3% and CD69: 78 ±8%) at 24 hours. For subjects receiving a second dose of acalabrutinib 12 hours after the first administration, full BTK target occupancy was observed 3 hours after the second dose for the 50-mg dosed cohort (BTK occupancy 97 ±4%).

ACE-HV-004 was a 3-part drug interaction study. Each part was conducted as an open-label, 2-period, fixed sequence study under fasting conditions. The study design was as follows:

- Part 1: In Period 1, a single oral dose of acalabrutinib (100 mg) was administered followed by PK sampling for 24 hours. In Period 2, a single oral dose of calcium carbonate (1 g) was coadministered with a single oral dose of acalabrutinib (100 mg) followed by PK sampling for 24 hours.
- Part 2: In Period 1, a single oral dose of acalabrutinib (100 mg) was administered followed by PK sampling for 24 hours. In Period 2, oral doses of omeprazole (40 mg) were administered QD for 5 consecutive days with a single oral dose of acalabrutinib (100 mg) coadministered on Day 5. PK sampling for acalabrutinib and omeprazole were done for 24 hours after dosing on Day 5.
- Part 3: In Period 1, a single oral dose of acalabrutinib (100 mg) was administered followed by PK sampling for 24 hours. In Period 2, oral doses of rifampin (600 mg) were administered QD for 9 consecutive days with a single oral dose of acalabrutinib (100 mg)

coadministered on Day 1 and Day 9. PK sampling for acalabrutinib and rifampin were done for 24 hours after dosing on Day 1 and Day 9.

Seventy-two healthy volunteers enrolled in the study. Acalabrutinib administration was well tolerated. Three AEs were reported as related to study drug. These were generalized pruritus, dyspepsia, and abdominal pain. All were considered mild and resolved without treatment. No drug-related AEs led to discontinuation from the study. No severe AEs or SAEs occurred on this study.

Coadministration of the gastric pH-modifiers calcium carbonate or omeprazole decreased mean  $C_{max}$  to 25% and 21% and AUC to 47% and 43%, respectively, of values obtained with acalabrutinib dosed alone. Rifampin dosed at 600 mg QD for 9 days decreased AUC to 23% of values obtained with acalabrutinib dosed alone. Results from Part 1 of this study suggest that subjects should avoid the use of calcium carbonate-containing drugs or supplements (e.g., antacids and calcium supplements) for a period of at least 2 hours before and after taking the study drug.

# 1.4.2 Safety of Acalabrutinib

This section includes preliminary safety in Study ACE-LY-005. Additional safety details in studies with healthy subjects and in subjects with malignancies are available in the acalabrutinib IB.

# 1.4.2.1 Safety of Acalabrutinib in Combination with Pembrolizumab for Subjects with B-Cell Malignancies (ACE-LY-005)

Study ACE-LY-005 is a Phase 1b/2, multicenter, open-label proof-of-concept study in subjects with B-cell malignancies. Safety data from 161 subjects are available as of the data cutoff date of 03 September 2017. Median exposure was 3.4 months (range 0.2 to 30.2 months).

All 161 subjects (100.0%) experienced at least 1 AE of any grade. The most frequently reported AEs were diarrhea (44.1%), headache (35.4%), fatigue (33.5%), cough (26.7%), nausea (26.7%), decreased appetite (24.8%), and vomiting (22.4%).

Nine subjects (5.6%) had Grade 5 (fatal) events, including 2 subjects with Grade 5 sepsis and 3 subjects with Grade 5 respiratory failure. One subject with DLBCL had Grade 5 neutropenic sepsis, which was considered by the investigator to be related to acalabrutinib. Two other subjects had Grade 5 events of respiratory failure and sepsis which were considered by the investigator to be related to pembrolizumab.

SAEs were reported for 73 subjects (45.3%). The most commonly reported SAEs were sepsis (5 subjects [3.1%]) and lung infection and AST increased (4 subjects [2.5%] each). Five subjects had SAEs reported by the investigator as related to only acalabrutinib of lymphoma, tumor flare, neutropenic sepsis (fatal event described above), nausea, and syncope.

Fifteen subjects had SAEs that were attributed to both acalabrutinib and pembrolizumab treatment. Of these 15 subjects, 1 subject experienced multiple related events of mental status change, pyrexia, lactic acidosis, and AST increased (Grade 3). Other SAEs related to both acalabrutinib and pembrolizumab were hypotension, dehydration, septic shock, systemic inflammatory response syndrome, ALT increased, Herpes zoster, lymphadenitis, cytokine release syndrome, lymphocyte count decreased, platelet count decreased, pancreatitis, pneumonitis, lymphoma, gastrointestinal hemorrhage, retroperitoneal mass, anemia, hyponatremia, upper gastrointestinal hemorrhage, enteritis, and neck pain.

Sixteen subjects had SAEs reported by the investigator to be related to only pembrolizumab, including AST increased, anemia, bronchitis, vertigo, orthostatic hypotension, drug-induced liver injury, platelet count decreased, sepsis, lung infection, pneumonitis, respiratory failure, respiratory distress, colitis, hyponatremia, pyrexia, tubulointerstitial nephritis, and systemic inflammatory response syndrome. The AE of drug-induced liver injury was attributed to pembrolizumab due to the known risk for pembrolizumab of immune-mediated hepatitis, and occurred in a subject in whom initial corticosteroid therapy was likely not adequate. The event improved when corticosteroids were again administered per guidance in the pembrolizumab prescribing information (Immune-Mediated Hepatitis, pembrolizumab prescribing information).

A total of 40 subjects (24.8%) had AEs that led to study drug discontinuation, the most frequent of which included ALT increased (8 subjects [5.0%]) and AST increased (7 subjects [4.3%]). One subject discontinued study drug due to an AE of lymphoma, considered by the investigator to be related to acalabrutinib only. Five subjects discontinued study drug due to AEs considered to be related to both acalabrutinib and pembrolizumab, including ALT increased in 2 subjects, and cytokine release syndrome, pneumonitis, and AST increased in 1 subject each. Thirteen subjects discontinued treatment due to AEs considered related

only to pembrolizumab, including 1 or more AEs of ALT increased, AST increased, pneumonitis, deafness neurosensory, neutropenia, bursitis, pneumonitis, colitis, and diarrhea.

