# 5.5 ENDPOINT DATA ANALYSIS

### 5.5.1 Safety Endpoint

Safety summaries will include summaries in the form of tables and listings. The frequency (number and percentage) of treatment-emergent AEs will be reported in each treatment group by MedDRA System Organ Class and Preferred Term. Summaries will also be presented by the severity of the AE (per CTCAE, v4.03 or higher) and by relationship to study drug (e.g., either acalabrutinib, pembrolizumab, or both).

Laboratory shift tables containing counts and percentages will be prepared by treatment assignment, laboratory parameter, and time. Summary tables will be prepared for each laboratory parameter. Figures of changes in laboratory parameters over time will be generated.

Results of vital sign assessments, ECGs, and physical examinations will be tabulated and summarized.

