9 STATISTICAL METHODS OF ANALYSIS

9.1 General Principles

Descriptive statistics will be used to summarize baseline demographic and disease characteristics, study drug administration, efficacy and safety outcomes. Descriptive summaries of discrete data will present the sample size and the incidence as a frequency and as a percentage. Descriptive summaries of continuous data will present

the sample size, group mean, standard deviation (SD), median, and range. Confidence intervals (CIs) may be included as appropriate.

Summary tables will be presented by disease types: CLL/SLL, MCL, WM, FL, GCB DLBCL, MM, non-GCB DLBCL, RICHTER's and Other (include unclassifiable DLBCL, double hit lymphoma, FL with transformation, mediastinal DLBCL, mediastinal gray zone lymphoma, non-hodgkin's lymphoma [NHL], non-mediastinal gray zone lymphoma, red pulp small B-cell lymphoma, triple hit high grade NHL, hodgkin's lymphoma, marginal zone lymphoma), unless otherwise stated.

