9.7.1 Adverse Events

The Medical Dictionary for Regulatory Activities (MedDRA) will be used to code all AEs to a system organ class and a preferred term. The severity of the AE will be assessed by National Cancer Institute (NCI) Common Terminology Criteria for Adverse Events (CTCAE) Version 4.03 or higher. Drug-related AEs are those assessed by investigator as related.

Treatment-emergent AEs are defined as those events that occur (actual or imputed start date) on or after the first dose of study drug, through the treatment phase, and within 30 days following the last dose of study drug.

Treatment-emergent AEs will be summarized by system organ class and preferred terms in descending order of frequency, by NCI toxicity grade and by relationship to study drug. The same summary will be provided for serious treatment-emergent AEs and drug-related serious treatment-emergent AEs, treatment-emergent AEs leading to treatment discontinuation, dose reductions and dose withheld.

Death information is reported in the study exit CRF for all deaths. Incidences of deaths are to be reported, along with the primary cause of death.

AE by subject listing and death listing will be provided.

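### Adverse events are tabulated by disease type only as crude counts and percentages over a window that lengthens with treatment, with no person-time rate and no timing of onset

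*Protocol*

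**What the plan says.** Both documents make safety the primary objective (Protocol 2.1, SAP 2.1). On how adverse events will be summarised:

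- Protocol 5.5.1: "The frequency (number and percentage) of treatment-emergent AEs will be reported in each treatment group".
- SAP 9.1 presents discrete data as a frequency and a percentage, and adds: "Summary tables will be presented by disease types". Nine disease groups are listed.
- SAP 9.7.1: "Treatment-emergent AEs will be summarized by system organ class and preferred terms in descending order of frequency", then by grade and relationship. The same summary is repeated for serious events, drug-related serious events, and events leading to discontinuation, reduction or withholding. An event is treatment-emergent if it starts between first dose and 30 days after last dose.
- SAP 9.5.3 summarises duration of exposure, but no section uses it as a denominator for adverse events. Kaplan-Meier estimation (SAP 9.6.6) is confined to duration of response, progression-free survival and overall survival.
- Protocol 3.1.1 names timing of onset and duration among the features that characterise safety. Neither SAP 4.1 nor SAP 9.7.1 carries them over, although SAP 10 reports no major departure from the protocol's analyses.

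On exposure, Protocol 1.4.2.1 reports: "Safety data from 161 subjects are available as of the data cutoff date of 03 September 2017", and "Median exposure was 3.4 months (range 0.2 to 30.2 months".

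**The concern.** A crude percentage gives the same weight to a subject observed for a week and one observed for two years. That is harmless when time at risk is similar in every column of a table. Here acalabrutinib continues until progression, unacceptable toxicity or the end of the trial, 48 months after the last enrolment (Protocol 3.0), and the event window follows it. If disease groups stay on treatment for different lengths of time, their columns in the primary safety tables mix the rate of toxicity with the length of observation.

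The any-event row cannot help, because all 161 subjects had already had at least one adverse event by September 2017. The rows that matter are serious events, higher grades, discontinuations and specific terms such as AST or ALT increase. In those rows a difference in treatment duration could be read as a difference in toxicity.

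**Working it through.** **Inputs from the documents**

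- Pooled exposure: median 3.4 months, range 0.2 to 30.2 (Protocol 1.4.2.1).
- Pooled crude proportions at the same cutoff: "Nine subjects (5.6%) had Grade 5 (fatal) events", 73 subjects with a serious event, and "A total of 40 subjects (24.8%) had AEs that led to study drug discontinuation".
- Event window: time on treatment plus 30 days, taken as 1 month (SAP 9.7.1).

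**Inputs assumed, because the documents do not give them**

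- Exposure by disease type: 2 to 24 months.
- Hazard shape: constant, or front-loaded (Weibull, shape 0.5).

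**Step 1. Reproduce the protocol's figures.** 73/161 = 45.3%, 9/161 = 5.6% and 40/161 = 24.8%. All three agree.

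**Step 2. One constant hazard in every group.** With hazard h per month and t months on treatment, P(at least one event) = 1 − exp(−h × (t + 1)). At an assumed h = 0.10:

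- t = 3.4: 1 − exp(−0.44) = 36%
- t = 12: 1 − exp(−1.30) = 73%
- t = 24: 1 − exp(−2.50) = 92%

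That is about a 2.6-fold spread with no difference in risk.

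**Step 3. Tie the hazard to the trial's pooled figures.** Set h so that the pooled percentage is met at median exposure: h = −ln(1 − p)/4.4. This is approximate, since the pooled figure averages over all exposures. For serious events h = 0.137 per month; for events leading to discontinuation h = 0.065. The front-loaded version replaces h × (t + 1) with c × (t + 1)^0.5, anchored at the same point.

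| Event class | Hazard | 3.4 months | 12 months | 24 months |
|---|---|---|---|---|
| Serious | constant | 45% | 83% | 97% |
| Serious | front-loaded | 45% | 65% | 76% |
| Leading to discontinuation | constant | 25% | 57% | 80% |
| Leading to discontinuation | front-loaded | 25% | 39% | 49% |

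The direction is the same under both shapes. The size depends heavily on the shape.

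**Step 4. Does a person-time rate remove the effect?** In a simulation with 30 subjects per group, exponential exposure plus the 1-month tail, and a true rate of 6.49 first events per 100 person-months in every group, median exposures of 2, 3.4, 12 and 24 months gave:

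- crude percentage: 21%, 29%, 56%, 71%
- events per 100 person-months: 6.4, 6.5, 6.5, 6.6

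**Step 5. Would a cumulative incidence do instead?** Take h = 0.10 in every group, the same four median exposures, and end of the treatment-emergent window as a competing event:

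- 12-month cumulative incidence: 30%, 38%, 57%, 63%
- crude percentage: 30%, 39%, 67%, 80%

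In the short-exposure groups it is almost the crude figure. A subject who leaves the window early is counted as never having the event, so the estimate still depends on exposure. The person-time rate stays at 10 per 100 person-months in all four groups.

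**The case against.** The case for leaving the plan alone has force.

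- **The range is not a range between groups.** It is a spread across individual subjects at an interim cutoff, about four months after enrolment closed in May 2017 (Protocol 5.1), so part of it is staggered entry. A reader might infer from 0.2 to 30.2 months that disease groups differ on that scale. The documents do not support this, because exposure by disease type appears nowhere. Protocol 1.1 says only that responses to single-agent BTK inhibitors can be brief in aggressive histologies. This part of the objection stands.
- **The direction is conditional.** A reader might infer that the cohorts responding longest will appear least safe and those progressing early safest. That requires equal underlying risk and exposure ended mainly by progression. About a quarter of subjects had events leading to discontinuation, so toxicity itself shortens exposure and can work the other way. This also stands.
- **No comparison is planned.** The study has no comparator, SAP 5 tests no hypothesis, and no contrast between disease types is specified. Crude incidence is a legitimate description of a safety profile. This limits the harm to descriptive reading across columns, but for the primary objective those descriptive tables are the whole analysis.
- **Other information is available.** Exposure is tabulated, adverse events are listed by subject, and SAP 9.7.2 plans shift tables and plots over time for selected laboratory parameters. None of these relates event frequency to time at risk, and a reader could not obtain time to first event by group without reanalysing the listings. This answers the point only in part.

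**Conclusion.** The gap is real and narrow. The planned TEAE summaries take no account of time at risk, the event window grows with treatment, and a safety parameter named in the protocol (timing of onset) has no analysis in the SAP.

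At equal underlying risk, a group treated longer would show higher crude percentages. How much higher in this trial is unknown. The 36%, 73% and 92% at 3.4, 12 and 24 months rest on an assumed constant hazard of 0.10 per month and assumed group exposures. With front-loaded events the spread shrinks; for serious events it is 45% to 76%, about 1.7-fold.

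The documents do not show that any disease group will be misrepresented, and no test, sample size or decision rule depends on this. It is a cheap improvement to the reporting of the primary objective.

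**What to change.** Keep the crude tables. In SAP 9.7.1 add the following, by disease type and overall, for Grade 3 or higher TEAEs, serious TEAEs, TEAEs leading to discontinuation, and AST/ALT increase:

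1. Person-months at risk, counted from first dose to the first event or the end of the treatment-emergent window, and the number of subjects with a first event per 100 person-months, with an exact Poisson 95% CI.
2. The same rate by interval since first dose (for example 0–3, 3–6, 6–12 and over 12 months), overall and by disease where numbers allow, so that a constant hazard is not assumed.
3. A summary of time to onset of the first event, which brings the SAP back into line with Protocol 3.1.1.

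Do not rely on cumulative incidence at 6 or 12 months, with end of the window as a competing event, as the exposure adjustment. Step 5 of the working shows that it still depends on exposure.

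The rates belong beside the crude percentages, not in their place, because toxicity can itself shorten exposure.

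Cost: one or two extra tables from dates already needed for the TEAE flag and the exposure summary, with no change to conduct or sample size. With 161 subjects in nine groups (161/9, about 18 each on average), the entries by disease will be sparse and the intervals wide.
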